### Primary Analysis Period

The time period from the enrollment date to the end of primary analysis period date, inclusive

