### Overall Study Period

If the study will continue to the final analysis, the overall study period is defined as the time period from the enrollment date to the end of final analysis period date, inclusive.

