#### Subject Incidence Rate for Adverse Events

The subject incidence rate for a given event in a given time period (double-blind period, primary analysis period, or overall study period) is defined as the number of subjects with  $\geq 1$  reported occurrence of the event divided by the number of subjects who are at risk for having the event in the beginning of the given time period. For subjects with multiple occurrences of the same event in a given period, the event will only be counted once per subject.

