### **Subject Years On-Study in Primary Analysis Period**

Defined for a given subject as the number of days between the first dose date to end of primary analysis period date, inclusive, divided by 365.25 (ie,  $[\text{End of Primary Analysis Period Date} - \text{First Dose Date} + 1] / 365.25$ ). The subject years on study will be summed over all subjects within a treatment group. For subjects who never received a dose of investigational product, the randomization date will be used.

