## **7.5 Safety Analysis Set**

This safety analysis set includes all randomized subjects who receive  $\geq 1$  active dose of investigational product in the 12-month double-blind ALN-controlled study period. This analysis set will be used to analyze safety data for the double-blind study period, primary analysis period, and overall study period. AEs that begin on the end of double-blind period date will not be included in the 12-month double-blind study period. AEs that begin on the date of the end of primary analysis study period will be included in the primary analysis study period. These subjects will be analyzed according to their actual treatment received, where subjects who received  $\geq 1$  dose of romosozumab will be analyzed in the romosozumab treatment group regardless of the randomized treatment. The subject incidence rates for the primary analysis study period include all events that occurred in the double-blind study period and all events occurred on and before the end of primary analysis date for those subjects who received at least one dose of open-label ALN.

If the study continues to the final analysis, the subject incidence rates for the overall study period include all events that occurred in the double-blind study period and all events occurred in the open-label ALN period for those subjects who received at least one dose of open-label ALN.

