### 10.6.1 Adverse Events

The Medical Dictionary for Regulatory Activities (MedDRA) version 19.1 or later will be used to code all adverse events to a system organ class and a preferred term for the 12-month double-blind period, the primary analysis period (at the primary analysis) , and the overall study period (at the final analysis). Adverse events will be summarized in the double-blind period, in the primary analysis study period (at the primary analysis), and overall study period (at the final analysis) for all subjects who receive at least one dose of investigational product in the double-blind period. The subject incidence rates for the primary study and overall study period will include all events that occurred in the double-blind period, and in addition, all events that occurred in the open-label period for those subjects who received at least one dose of open-label ALN.

All adverse event tables will be summarized by actual treatment group. The subject incidence of adverse events will be summarized for all treatment-emergent, serious, treatment-related, serious treatment-related, those leading to withdrawal of study, leading to withdrawal of investigational product, fatal, and of special interest. Subject incidence of special interest adverse events will also be summarized according to their categories.

Subject incidence of all treatment-emergent, serious, treatment-related, serious treatment-related, those leading to withdrawal of study, leading to withdrawal of investigational product, and fatal adverse events will be tabulated by system organ class and preferred term in descending order of frequency. Subject incidence of all treatment-emergent adverse events will be tabulated by system organ class, high-level group term, and preferred term in descending order of frequency as well as by preferred term.

Summaries of treatment-emergent adverse events occurring in at least 5% of the subjects and serious treatment-related adverse events occurring in at least 0.1% of the subjects will be provided by preferred term in descending order of frequency.

Treatment-emergent adverse events occurring in at least 2% of the subjects and also

have a >1% difference than ALN will also be summarized by preferred term in descending order of frequency.

Subgroups group analyses for age strata (< 75, ≥ 75 years) will be presented by system organ class and preferred term in descending order of frequency.

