Summaries of abnormal laboratory values, including summaries of shifts, worst post-baseline calcium, and evaluation of potential Hy's law cases will be summarized in the double-blind period and in the primary analysis period for all subjects who receive at least one dose of investigational product in the double-blind period. The subject incidence rates for the 24-month study period will include all laboratory measurements collected in the double-blind period, and in addition, all laboratory measurements collected in the open-label period for those subjects who received at least one dose of open-label alendronate.

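### Later-period safety incidences count events after the double-blind period only in women who took open-label alendronate, over a denominator that includes everyone

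*SAP*

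**What the plan says.** SAP 7.5 defines one safety set and states: "This analysis set will be used to analyze safety data for the double-blind study period, primary analysis period, and overall study period". For the primary analysis period it counts all double-blind events plus "all events occurred on and before the end of primary analysis date for those subjects who received at least one dose of open-label ALN". It sets a parallel rule for the overall study period.

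SAP 10.6.1 repeats the rule for adverse events, adding "all events that occurred in the open-label period for those subjects who received at least one dose of open-label ALN". The same paragraph says that the tables cover everyone dosed in the double-blind period. SAP 10.6.9 does likewise for laboratory abnormalities, adding "all laboratory measurements collected in the open-label period for those subjects who received at least one dose of open-label alendronate".

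The denominator is defined in SAP 6.3. Subjects with the event are "divided by the number of subjects who are at risk for having the event in the beginning of the given time period", and that definition names the primary and overall periods among those it governs. SAP 6.1.3 starts both at enrollment. The primary analysis period is "The time period from the enrollment date to the end of primary analysis period date, inclusive"; for the longer one, "the overall study period is defined as the time period from the enrollment date to the end of final analysis period date, inclusive".

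SAP 10.6 plans a listing of post-double-blind events for subjects who remained on study without open-label ALN.

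**The concern.** The numerator is restricted by something that happens after randomisation, and the denominator is not. Protocol 6.5 and 8.1 ask women who stop investigational product to stay under observation, so the group left out of the numerator is expected to exist. The planned listing confirms that the SAP anticipates it.

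Two things are at stake. First, the reported later-period incidences are too low whenever one of these women has a first event after the double-blind period. Second, whether a woman goes on to open-label ALN may depend on how she fared in the first year. If the share who do not, or their risk, differs by arm, the between-arm comparison of harms shifts. Fracture efficacy at the primary analysis is counted in all randomised subjects regardless of treatment received (SAP 7.2, 10.1). Benefit and harm over the same period would then rest on different bases.

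**Working it through.** **Definitions set side by side.** The plan states no safety incidence, so there is no figure to reproduce.

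| Element | Rule | Source |
|---|---|---|
| Population | One safety set for all three periods | SAP 7.5, 10.6.1 |
| Denominator | At risk at the start of the period, which is enrollment | SAP 6.3, 6.1.3 |
| Numerator, double-blind | All events in the safety set | SAP 7.5 |
| Numerator, later | Only women with at least one open-label ALN dose | SAP 7.5, 10.6.1, 10.6.9 |
| Later events of the others | Listing only | SAP 10.6 |

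For a woman who never takes open-label ALN, SAP 6.1.2 ends the double-blind period by Study Day 396 at the latest. After that she can add nothing to the numerator. An event starting on the end date itself is excluded from the double-blind period by SAP 7.5, so for her it is counted in neither part.

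**Comparison with the protocol.** Protocol 10.5.2.2 summarises AEs in the primary and overall periods by the same approach as the 12-month period, with no ALN condition. SAP Section 11 does not list the restriction as a change.

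**Size (illustration only).** Let f be the share of the safety set on study after the double-blind period without open-label ALN, and q the chance that such a woman's first event falls in that later time. Then

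reported incidence = incidence counting everyone followed − f × q.

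Inputs for q:
- Assumed event rate r = 2% per year.
- Assumed relative risk of non-takers k = 1 to 3.
- Mean time at risk after Month 12, T. Protocol 3.4.1 gives 25 to 59 months per subject to the primary analysis. Taking off about 1 month of screening and 12 months of double-blind treatment leaves 12 to 46 months. With uniform enrolment (assumed) and the plan's 8% yearly dropout, T is about 2.17 years.

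q = exp(−r) × (1 − exp(−k·r·T)), where exp(−r) is the chance of no event in year one.

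| k | q | f = 1% | f = 2% | f = 5% |
|---|---|---|---|---|
| 1 | 4.16% | 0.042 points | 0.083 points | 0.208 points |
| 3 | 11.95% | 0.119 points | 0.239 points | 0.597 points |

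The range of 0.04 to 0.60 points is 0.8 to 12 subjects in an arm of 2,000.

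A second set of assumptions takes double-blind risk a = 2% to 5%, later risk in takers b = 3% to 5%, f = 2% to 10% and k = 1 to 2. The shortfall is (1 − a) × f × b × k. It runs from 0.95 × 0.02 × 0.03 × 1 = 0.06 points to 0.98 × 0.10 × 0.05 × 2 = 0.98 points.

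**Between arms.** If f and q are equal in both arms, the shortfalls are equal. With f = 2% in one arm and 5% in the other, they differ by 0.208 − 0.083 = 0.125 points (k = 1) or 0.597 − 0.239 = 0.358 points (k = 3). The documents give no basis for saying which arm would have the larger f.

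**The case against.** The strongest defence is that the rule is deliberate and disclosed. The safety objective concerns romosozumab followed by ALN, and the rule is stated three times with a listing for the women it leaves out. Under Protocol 6.5 and 8.1, a woman who stops investigational product may start another osteoporosis therapy, so her later events may lie outside the sequence being characterised.

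This could justify a supportive table, but not the mixed rate. Nor is the rule a consistent on-treatment rule: one open-label dose is enough for all of a woman's later events to count to the end of the period. Restricting the denominator to takers from enrollment would not repair it, because that selects women who remained for about a year and mishandles the double-blind events of the others. For Month 12 to 24 efficacy, the SAP restricts the whole analysis set to takers (7.10) and warns about the non-randomised comparison (10.5.3.1). The safety rule does neither.

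A second objection stands. Protocol 9.1.2 collects AEs to end of study. Protocol 9.2.2 and Appendix A note 12 run SAE reporting to 30 days after the last dose, after which active monitoring for SAEs is not required. For a woman without open-label ALN, the last dose falls in the double-blind period. Counting her recorded SAEs may therefore still give an incomplete number.

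A reader might also infer that cardiovascular comparisons are affected, or that the omitted events disappear. The documents do not establish either. SAP 10.6.3 names neither the periods nor the ALN condition, so its coverage is an inference from 7.5. The omitted AEs are listed, and deaths should also appear as withdrawal reasons in the disposition table (SAP 10.2). The primary-period subject-years ("the number of days between the first dose date to end of primary analysis period date, inclusive") carry no ALN condition either, but no analysis in SAP 10.6 uses them, so no planned table is shown to have that mismatch.

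**Conclusion.** The concern holds for the primary-period and overall-period safety incidences. Numerator and denominator refer to different groups. The direction for incidence is certain: too low whenever a woman on study without open-label ALN has a first event after the double-blind period, and unaffected otherwise. The effect on the arm comparison is possible but of unknown direction. A reader might infer a bias in favour of romosozumab; nothing in the documents supports that.

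The size is probably small. The 0.04 to 0.60 point range rests entirely on assumed f, r and k, and the wider assumptions reach about 1 point. The plan intends no statistical testing of safety unless specified. The cost of correction is low and the output is comparative safety, so the change should be made. Confidence is medium, because the number of women concerned is not known.

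**What to change.** 1. In the primary-period and overall-period incidence tables (AEs, SAEs, deaths, and adjudicated cardiovascular events if shown for those periods), count all recorded on-study events of all safety-set subjects, regardless of open-label ALN.
2. Keep the ALN-conditioned summary as supportive only. Limit it to events and person-time from the start of the open-label period, use open-label ALN takers as the denominator, and attach the caution on non-randomised comparison from SAP 10.5.3.1.
3. Report by arm the number on study without open-label ALN. The planned disposition and exposure summaries give this only in part.
4. Reconcile the AE and SAE reporting windows (Protocol 9.1.2 against 9.2.2 and Appendix A note 12). Until then, state that later SAE counts in women without open-label ALN may be incomplete.

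Minor wording: state in SAP 10.6.3 which periods are covered. Correct the 24-month label in 10.6.9, where the summaries are for the primary analysis period. Use one safety-set definition: SAP 7.5 and 10.6 require an active dose, while SAP 10.6.1 and Protocol 10.1.6.5 require any dose of investigational product, which includes placebo under Protocol Section 6. List any change from the protocol in SAP Section 11.

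The cost is SAP wording and one extra set of tables, using events already recorded and listed. The small downside is that some counted events will occur off study drug or on another osteoporosis therapy.

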## **7.6 Primary Efficacy Analysis Set for BMD, Height, and PRO/ClinRO Endpoints for the Double-blind ALN-controlled Study Period and Primary Analysis Period**

This analysis set includes all randomized subjects who have a baseline and  $\geq 1$  post-baseline evaluation at or before the time point under consideration. Note that this subset could potentially be different from endpoint to endpoint due to missing data. Subjects in this subset will be analyzed according to their randomized treatment assignment, regardless of treatment received.

## **7.7 Analysis Set for Post Fracture PRO/ClinRO Endpoints**

This analysis set includes all randomized subjects who experienced a nonvertebral or clinical vertebral fracture in the double-blind period and have a pre-fracture baseline and  $\geq 1$  post fracture evaluation at or before the time point under consideration. Note that this subset could potentially be different from endpoint to endpoint due to missing data. Subjects in this subset will be analyzed according to the randomized treatment assignment.

## **7.8 Analysis Subsets for Imaging and Pharmacokinetics (PK) / Bone Turnover Marker (BTM) / Biomarker Sub-study**

### **7.8.1 Sub-study Imaging Efficacy Analysis Set**

The respective subset includes all randomized subjects who enrolled in the sub-study and have a baseline and  $\geq 1$  post-baseline evaluation at or before the time point under consideration and will be used to evaluate vBMD, bone strength measure by FEA and DXA BMD. Subjects will be analyzed according to their randomized treatment assignment.

### **7.8.2 Sub-study BTM Efficacy Analysis Set**

The subset includes all randomized subjects who enrolled in the sub-study who have a baseline and  $\geq 1$  post-baseline reported BTM result at or before the time point under consideration and will be used to evaluate P1NP, BSAP, OC and sCTX. Subjects will be analyzed according to their randomized treatment assignment, regardless of treatment received.

### 7.8.3 Sub-study BTM Safety Analysis Set

The subset includes all randomized subjects who enrolled in the sub-study who receive  $\geq 1$  dose of investigational product, have a baseline and  $\geq 1$  post-baseline reported BTM result at or before the time point under consideration and will be used to evaluate iPTH and serum sclerostin level. Subjects will be analyzed according to the actual treatment received, where subjects who received  $\geq 1$  dose of romosozumab will be analyzed in the romosozumab treatment group regardless of the randomized treatment.

### 7.8.4 Sub-study PK Analysis Set

The subset includes all randomized subjects who enrolled in the PK sub-study, receive  $\geq 1$  dose of romosozumab, and have  $\geq 1$  reported result. Subjects will be analyzed according to their actual treatment received.

## 7.9 Subgroup Analyses

The new vertebral fracture through Month 12 or Month 24, clinical fracture and nonvertebral fracture through Month 12 or at primary analysis, will be analyzed within each of the following subgroups:

- Age ( $< 75$  years,  $\geq 75$  years)
- Presence or absence of severe vertebral fracture at baseline (based on most severe Genant semiquantitative grade at baseline on screening spinal radiograph)
- Number of prevalent vertebral fractures at baseline (0-1, 2,  $\geq 3$ ; based on screening spinal radiograph)
- Race (White and non-White)
- Geographic region
  - Western Europe and New Zealand/Australia
  - Central and Eastern Europe and Middle East
  - Asia Pacific and South Africa
  - North America
  - Central/Latin America
- Central/Latin America and all regions excluding Central/Latin America
- Baseline lumbar spine BMD T-score ( $\leq -3$ ,  $> -3$  and  $\leq -2.5$ ,  $> -2.5$ )
- Baseline total hip or femoral neck BMD T-score  $\leq -3$  vs both total hip and femoral BMD T-score  $> -3$

- Baseline BMI (tertiles)
- FRAX score for major osteoporotic fracture (tertiles)
- History of nonvertebral fracture at age  $\geq 55$  years (yes, no)

The percent changes from baseline in lumbar spine BMD and total hip BMD at month 12 and month 24 will be analyzed by the following subgroups:

- Age ( $< 75$  years,  $\geq 75$  years)
- Geographic region
- Baseline lumbar spine BMD T-score ( $\leq -3$ ,  $> -3$  and  $\leq -2.5$ ,  $> -2.5$ ; for lumbar spine BMD analysis only)
- Baseline total hip BMD T-score ( $\leq -3$ ,  $> -3$  and  $\leq -2.5$ ,  $> -2.5$ ; for total hip BMD analysis only)

These subgroups, except for age strata, will be re-examined for appropriateness and may be re-categorized or omitted (due to small sample size, for example, if there are  $< 10\%$  of subjects within a subgroup) before unblinding. The analyses of these subgroups will be exploratory in nature.

#### **7.10 Efficacy Analysis Set in Month 12 to 24 Study Period**

This set includes all randomized subjects who received at least one open-label ALN dose. Subjects in the analysis set will be analyzed according to their randomized treatment assignment, regardless of treatment received. The analysis set will be used as the primary analysis set for the following endpoints between Month 12 and Month 24: nonvertebral fracture, clinical fracture, clinical vertebral fracture, and hip fracture.

#### **7.11 Efficacy Analysis Set for Vertebral Fracture in Month 12 to 24 Study Period**

This analysis set includes all randomized subjects who received at least one open-label ALN dose and have evaluation of vertebral fracture at Month 12 and at or before Month 24. This analysis set will additionally include subjects who have vertebrae with missing Genant semiquantitative scores prior to Month 12 and whose first spinal radiograph after Month 12 shows no fracture on the same vertebrae because it can be inferred that the baseline and Month 12 scores would have also shown no fracture had they been available. This analysis set will be used as the primary analysis set for new vertebral fracture between Month 12 and Month 24.

## 8. Interim Analysis and Early Stopping Guidelines

No formal interim analysis is planned for this study prior to the evaluation of the primary endpoints.

An external, independent DMC will monitor unblinded safety data on an ongoing basis throughout the entire study period and, if a potential safety signal is identified, may consider efficacy data in order to assess the risk/benefit profile of romosozumab. DMC members will have access to treatment assignments if knowledge of treatment assignment at the individual level is essential to evaluate safety. To minimize the potential introduction of bias, these individuals will not have direct contact with the study site personnel or subjects. An independent statistical service provider will generate unblinded reports for review by the DMC. If at any time there are safety concerns, the DMC will communicate the concerns to a representative from Amgen senior management. The DMC will convene approximately every 3 to 6 months. The start date will depend on the subject accrual rates. Roles and groups requiring access to restricted and interim data at the time of the primary analyses and any time before initial database lock will be pre-specified to ensure the integrity of the trial.

Records of all meetings will be maintained by the DMC for the duration of the study. Records of all meetings will be stored in the Amgen official document management system Trial Master File at the conclusion of the study. Further details are provided in the DMC Charter.

Staff from the Pharmacokinetics and Drug Metabolism group will be unblinded to treatment assignments before study final unblinding to perform exposure-response analyses. These individuals will ensure potentially unblinding data are not distributed to blinded individuals until the study is unblinded.

Early access to data for exposure-response analysis is solely for the purpose of preparing datasets and statistical programs (ie, administrative processing). Any in-process results from this early access will not be distributed and do not constitute an interim analysis.

## **9. Data Screening and Acceptance**

### **9.1 Data Handling and Electronic Transfer of Data**

All data for this study will be received from Amgen's data management department and will be housed within the Electronic Data Capture (EDC) database, RAVE. All screening and on-study blood samples will be processed by the central laboratory (with the exception of the serum electrophoresis samples that are processed/analyzed by a local laboratory) and will be electronically transferred to the Amgen database. All imaging data (eg, X-ray, QCT, FEA, and DXA), will be submitted to the central imaging vendor for final analysis. The results from the central imaging vendor analysis will be electronically transferred to the Amgen database. All other data will be captured on the eCRF.

An Analysis Dataset for Pharmacokinetics Concentrations (ADPC) will be provided to the Clinical Pharmacology, and Modeling and Simulation group from Biostatistics.

